3.1.5. Study Environment

Research visits and the medication dosing session will be conducted at Harborview Medical Center. The screening, consent, preparation, and integration visits will occur at the Virology Research Clinic at Harborview Medical Center in the Ninth and Jefferson Building on the 11th floor. These visits will occur in a clinic room designed for outpatient, non-procedural visits, and this is a private room that is equipped with comfortable chairs and a window, appropriate for psychotherapy visits. This clinic is dedicated research space that is a non-CRBB space and is directed by [name].

The medication sessions will occur at Harborview Medical Center, in the Sleep Lab. These research visits will occur during the day when the clinic is not in session, in a room used for nighttime sleep studies. These are private, quiet rooms that are outfitted like hotel rooms with minimal equipment, a comfortable bed, art prints on the walls, chairs for therapists, and a private bathroom.

3.1.6. Study Enrollment and Withdrawal

Participant Population – physicians and nurses with moderately severe symptoms of depression. Participants meeting study inclusion / exclusion criteria after careful screening and examination will be invited to participate and will be provided with all the information needed to provide an informed consent. We will recruit 30 adult participants (25 to 65 years) of both sexes with clinically significant symptoms of depression.

4. Participant Inclusion and Exclusion Criteria

4.1. Inclusion Criteria

- a. Participants must be physicians or nurses or advance practice providers (nurse practitioners or physician assistants) with at least 1 month of frontline clinical experience during the COVID pandemic who rate at least 2 of 4 items from the COVID Exposure index as 'more than half the days' during their peak 2 week period of exposure:
 - i. Caring for someone critically ill with COVID-19, or who became critically ill while you were involved.
 - ii. Working longer hours than usual in order to provide assistance or care to individuals with COVID-19
 - iii. Witnessing or responding to a death related to COVID-19, or losing a patient you had been caring for to COVID-19
 - iv. Caring for patients who have died without family physically present due to COVID-19 precautions

- b. Have a Montgomery-Asberg clinician-administered depression score \geq 21, indicating moderately severe symptoms. This measurement is clinician-administered and will be performed by a study team member who is not a therapist, who will receive special training.
- c. Have had persistent symptoms despite at least one medication and/or therapy trial of standard care treatment for depression.
- d. English speaking able to understand the process of consent and the risk and benefits associated with the study, and able to give written informed consent.
- e. Must be willing to sign a medical release for the investigators to communicate directly with their therapist and doctors to confirm a medication and/or medical history. This is decided on a case by case basisupon the discretion of the PI.
- f. Must be driven home after the medication dosing session by a driver(which could be a friend, family, rideshare or taxi).
- g. Must provide at least one adult to have continuous contact with the participant, provide participant transportation, monitor changes in the participant's behavior, and notify research staff of behavior changes.
- h. Has been off selective serotonin inhibitors for five half-lives of the drug plus 2 weeks.
- i. Must avoid taking any psychiatric medications or starting a new psychiatric medication during the study. Should participant's doctor recommend starting a new psychiatric medication, participant will be required to notify the study team and the subject would withdraw from the study
- j. Must provide a contact (relative, spouse, close friend, or other caregiver) who is willing and able to be reached by the Clinical Investigators in the event of a participant becoming suicidal.
- k. Must have a negative pregnancy test at study entry and prior to each medication dosing session if able to bear children and must agree to use adequate birth control.
- Are willing to commit to preparation sessions, medication dosing sessions, integration sessions, to complete evaluation instruments and commit to be contacted for all necessary telephone contacts.

4.2. Exclusion Criteria.

- a. Personal or immediate family history of schizophrenia, bipolar affective disorder, delusion disorder, paranoid disorder, or schizoaffective disorder.
- b. Suicidal ideation with a C-SSRS > 3
- c. Current substance abuse disorder (except in the case of mild alcohol use)
- d. Neuroleptic and SSRI medications that cannot be tapered and discontinued in conjunction with the participant's prescribing physician.
- e. Unstable neurological or medical condition; history of seizure, chronic/severe headaches.
- f. Positive urine pregnancy test at the time of screening
- g. Any unstable medical condition that my render study procedures unsafe based on the medical history performed as part of the screening procedures, including active cardiac medical issues such as ongoing angina, uncontrolled hypertension, or recent cardiac ischemia requiring medical attention (within the past 3 months
- h. Any use of psychedelic drugs within the prior 12 months.
- i. Use of tramadol, due to the potential for serotonin syndrome with concomitant use of

Page 23 Version 1.16, July 18, 2022

psilocybin.

- j. Allergy to niacin (N.B. the investigators will inform participants that flushing, redness, tingling, and headache are normal side effects that do not predict anaphylaxis, which although reported is extremely rare).
- k. Individuals who are on MOAI (monoamine oxidase inhibitors) or who have a known sensitivity to the drug or its metabolites. Psilocybin is contraindicated in medications that are known UGT (UDP-glucuronosyltransferase) enzymemodulators. The concurrent use of SSRI/SNRI meds is assumed to be contraindicated due to the potential to increase the risk of serotonin syndrome and/or to attenuate the binding of psilocin to the HT2A receptor.

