Anxiety. The most likely potential adverse effect of psilocybin is anxiety, or possibly panic, delusion, and cognitive impairments, particularly at higher doses (> 25 mg po) during the period of acute drug action. In recent studies of psilocybin in healthy humans conducted over the past 15 years, no adverse reactions other than the expected occasional episodes of fear or anxiety during the time of drug effect have been reported. Such transient episodes of fear or anxiety respond well to reassurance and have not required pharmacological intervention. Some individuals have been reported to develop paranoid and psychotic states while under the influence of psilocybin.

Insomnia. Although rare, insomnia following psilocybin administration has been reported in the literature; it has been described as self-limiting and responded well to reassurance from the study team.⁴¹ In the event that a participant experiences insomnia, a study physician may initially prescribe a sleep aid (i.e. diphenhydramine or hydroxyzine) and if the initial reassurance, education about sleep hygiene and pharmacological intervention was unsuccessful, a one-time dose of short-acting benzodiazepine (specifically lorazepam) and/or zolpidem will be considered.

1.3.3.1.d. Prolonged side effects

There is the possibility of prolonged adverse psychological reactions, such as psychosis and depression. It is generally believed that individuals with previous psychiatric conditions, particularly psychosis or mania, are at an increased risk for hallucinogen-induced psychosis.²⁹ Thus, psilocybin administered to a participant with a history of psychosis or mania could precipitate enduring psychiatric illness such as schizophrenia. This risk is very low, but cannot be excluded completely.⁴⁷ For this reason, all potential participants with personal or family histories of Schizophrenia, Psychotic Disorder, or Bipolar I or II disorder are to be excluded from participation. Nevertheless, although the risk is believed to be minimal, it is possible that some participants may develop a brief intense psychological reaction while under the influence of psilocybin.

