1.3.3.2. Potential risks of Niacin (active-placebo-control agent)

A participant's symptoms of depression or burnout could change or perhaps worsen during the course of the study, as symptoms might change if that individual were not participating in the study. However, there is no reason to believe that niacin &an active-placebo-control would exacerbate symptoms of depression or burnout. Niacin has expected physiological side effects that make it well suited to be used as an active placebo, including flushing, tingling, itching, and redness of the face, arms, and chest, as well as headaches, and these are documented to be transient. Other minor, transient, and occasional side effects include upset stomach, intestinal gas, and dizziness. Participants will be informed about these potential side effects, and they will be monitored throughout the drug administration visits.

1.3.3.3. Potential risks of changes or delay in participant treatments being received prior to screening

Participants will be asked to refrain from starting new medications, including OTC supplements, during the procedures involved in this study. Should circumstances warrant a change in treatment, then participants will be asked to immediately notify the study team. If medically warranted, the participant begins to experience a decline, or their provider believes a treatment change is necessary, then the participant will be withdrawn from the study and encouraged to seek treatment.

For participants who are tapering and discontinuing antidepressant medications prior to entering the study, the following safety measures will be taken:

- Participants will be required to discuss changes in their antidepressant medication with their own prescribing provider, and to provide the study staff with a written note from the provider describing the plan.
- Study staff will be in contact with a participant who is tapering their antidepressant medication weekly with a phone safety assessment that will involve use of the C-SSRS. (These safety assessments are not designated as a 'study visit' so do not appear in the study visit flowsheets in Section 3.1 that summarize research procedures).
- Participants will be required to provide the name of at least one adult who will be in continuous contact with them during the taper and discontinuation period.

1.3.3.4. Risk of Emotional Responses, Discomforts During Administration & follow-up meetings.

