4.3. Medication management

Medication contraindications will include anti-seizure medications, insulin and oral hypoglycemics, certain hypertension medications (clonidine, and aldomet specifically), cardiovascular medications and the following psychotropic medications: anti-psychotics (first and second generation agents), anti-depressants and mood stabilizers. Psychotropic medications cannot be taken in the previous two weeks, with Prozac (fluoxetine) not being taken within the last 5 weeks prior to receiving any study agents. Participants may only take prn (as needed) benzodiazepines (i.e., lorazepam) up to three days before the session.

Participants will refrain from taking any medications the day of medication dosing session, except prescribed opiate pain medication or over-the-counter non-narcotic pain medication at any time. It will also be necessary to refrain from alcohol the day before, the day of, and the day after each medication dosing session.

Participants must agree to:

- a. Ingest only alcohol-free liquids after 24:00 (midnight) the evening before the Medication Dosing Session
- b. Refrain from the use of any exclusionary medications. Except in the case that the PI prescribes benzodiazepine or zolpidem for insomnia.
- c. Refrain from use caffeine or nicotine for two hours before and six hours after ingesting the drug, or until research staff deem it safe to do so.

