6.2. Study schedule for participants by visit

6.2.1. Screening and Informed consent

Prior to participation in this research, subjects will receive a brief secure online screening survey and then if eligible, will be screened by phone to determine preliminary eligibility. All subjects will be informed about the phone screening and what the screening process involves.

All potential participants will be told that we collect demographic information, relevant medical history, and psychiatric history during the screening process. Screening data are entered directly into a secure online database and are considered a source document.

All seemingly eligible subjects will be told that they need to come in for baseline screening visit, and will be informed about baseline questionnaires, clinician assessment, blood draw, and pregnancy test (if applicable) to ensure their eligibility. Subjects are free to decline participation at this point or to discontinue participation at any future point and to withdraw from consideration.

Some potential participants live in another state, and it may not be feasible to have them come for an in-person screening visit. In this case we will conduct the screening interview uligescure video communication platforms. We will ask these participants to send us their most recent physical, and blood work (recent as of 1 month from the screening visit will be allowed). This will be faxed to the PI and reviewed for potential participation. A remote urine test will be ordered for the screening process of remote participants.

Prior to obtaining informed consent, the PI will confirm that the participant meets all study inclusion and exclusion criteria. The investigator or research staff member obtaining consent will ask the participant to provide a brief summary of the study to ensure they understand what is being asked of them and any potential risks and benefits.

Note that if a female subject is pregnant, or breast-feeding, or does not agree to use an approved birth control method (i.e., oral, injectable, or implant birth control, condom, diaphragm with spermicide, intrauterine device, tubal ligation, abstinence, or partner with vasectomy) she will be excluded.

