Findings of pregnancy, active cardiac medical issues, abnormal liver function, abnormal renal function, or abnormal blood counts, and any lab indicating an undiagnosed illness would exclude a participant from moving on to the preparation 1 visit. When screening requirements have been met, participants will have a visit with the PI and/or key study personnel in which the study, the scheduling and the procedures will be reviewed. All participants' questions will be answered prior to obtaining an informed consent.

After providing informed consent, the participant will complete initial measures. Note that randomization to the psilocybin or control (niacin) treatment groups will occur at the end of visit 2.

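### The risk section and exclusion criterion 4.2(a) word the psychosis exclusion differently, so a person barred by one can pass the other

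*Combined protocol and SAP*

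**What the plan says.** Section 1.3.3.1.d (prolonged side effects) warns that psilocybin could bring on lasting psychiatric illness in someone who has had psychosis or mania. It rates the risk as very low without ruling it out, and for that reason states that "all potential participants with personal or family histories of Schizophrenia, Psychotic Disorder, or Bipolar I or II disorder are to be excluded from participation".

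Section 4.2, the list headed as the exclusion criteria, puts the matter in item (a): "Personal or immediate family history of schizophrenia, bipolar affective disorder, delusion disorder, paranoid disorder, or schizoaffective disorder".

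Section 6.2.1 has the principal investigator confirm, before consent, that every inclusion and exclusion criterion is met, and the schedule in section 3.1 lists that review at screening. Sections 6.1 and 6.3 have placebo participants screened again against the study criteria before open-label psilocybin.

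On drugs, section 4.3 lists among its contraindications "certain hypertension medications (clonidine, and aldomet specifically), cardiovascular medications". Section 3.1.4 gives nearly the same list and adds that the two named antihypertensives are singled out because they act on the central nervous system.

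**The concern.** The exclusion in 1.3.3.1.d is the protocol's own answer to the most serious lasting psychiatric harm it describes. If the criterion used at screening is narrower than the statement it is meant to carry out, someone who follows 4.2(a) exactly can admit a person whom the risk section says must not take part. That matters first for participant safety. It also matters for describing the population studied, and for deciding whether a given enrolment was an eligibility deviation, since the answer depends on which section is read.

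The comparison between arms is not at stake. Eligibility is settled before randomisation and the primary analysis follows the intent-to-treat principle, so a participant admitted under the narrower wording does not bias the treatment contrast.

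**Working it through.** No arithmetic applies. The check is whether each kind of history is treated alike in the two passages, and whether another item in 4.2 closes any gap.

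| History | Section 1.3.3.1.d | Criterion 4.2(a) |
|---|---|---|
| Schizophrenia, own | Excluded | Excluded |
| Bipolar disorder, own | Excluded | Excluded |
| Delusional, paranoid or schizoaffective disorder, own | Excluded, if these count as psychotic disorder | Excluded by name |
| Past brief, substance-induced or unspecified psychotic disorder, own | Excluded as psychotic disorder | Not named |
| Schizophrenia in an immediate relative | Excluded | Excluded |
| Another psychotic disorder in an immediate relative | Excluded | Not named |
| Schizophrenia in a more distant relative, such as a cousin | Excluded, as family is not limited | Not excluded |

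The passages agree on schizophrenia and bipolar disorder in the person or an immediate relative. They disagree in the fourth, sixth and seventh rows. Neither passage defines family or immediate family.

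Depression with psychotic features is a further unclear case. The reason given in 1.3.3.1.d, a history of psychosis, covers it. Whether the category label covers it is open to argument, and 4.2(a) does not name it.

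Next, the other exclusion items, for a person whose past episode has resolved and who takes no antipsychotic:

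- 4.2(b) concerns suicidal ideation.
- 4.2(c) concerns a current substance disorder, so a past substance-induced episode is not caught.
- 4.2(d) concerns drugs that cannot be stopped.
- 4.2(e) and (g) concern unstable medical or neurological conditions, seizures and headaches.
- 4.2(f) concerns pregnancy.
- 4.2(h) concerns psychedelic use in the prior 12 months.
- 4.2(i), (j) and (k) concern tramadol, niacin allergy, and interacting drugs or drug sensitivity.

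None of these turns on a past psychotic episode or on a relative's diagnosis. Section 4.3 does not help either, because it bars current and recent drugs, not past diagnoses. The gap in 4.2(a) is therefore not closed elsewhere in the list.

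The secondary point is one of scope. Sections 3.1.4 and 4.3 both name two antihypertensives and then bar cardiovascular drugs without qualification. The text does not say whether the general term takes in the remaining antihypertensives, in which case naming two adds nothing, or whether it leaves them out.

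**The case against.** The best defence is that 4.2(a) already names the main psychotic-spectrum diagnoses and that screening does not rest on the list alone. Section 6.4 involves a psychiatrist in screening and evaluating every participant. Section 1.3.3.8 promises thorough screening for contraindicated psychological conditions, the schedule includes a mental health evaluation, and section 4.5 allows withdrawal in the participant's interest. No clause says that 4.2 prevails over 1.3.3.1.d. This stands as far as it goes: what is missing is the residual category and the wider family scope, and such a person might well be stopped. It does not remove the mismatch, because those safeguards depend on the assessor remembering a sentence in the background section.

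A reader might infer several stronger things that the documents do not support.

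- That other exclusions are also lost because 4.2 omits them. Section 6.2.1 provides that "abnormal liver function, abnormal renal function, or abnormal blood counts, and any lab indicating an undiagnosed illness would exclude a participant" from going on to the first preparation visit. It also excludes a candidate "if a female subject is pregnant, or breast-feeding, or does not agree to use an approved birth control method". Both rules bind before randomisation, so their absence from section 4 is a matter of layout.
- That the age range is a missing safety limit. "We will recruit 30 adult participants (25 to 65 years) of both sexes" is a recruitment statement, and nothing links age to dosing risk.
- That item (d) opens a further gap, because it excludes "Neuroleptic and SSRI medications that cannot be tapered and discontinued in conjunction with the participant's prescribing physician" while the safeguards in 1.3.3.3 begin "For participants who are tapering and discontinuing antidepressant medications prior to entering the study, the following safety measures will be taken". Item (d) and section 4.3 are compatible, stopping a drug does not waive 4.2(a), and whether those safeguards should reach other drug classes is a clinical decision on which the passages do not contradict each other.
- That a person with controlled hypertension on another drug is both eligible and ineligible. Exclusions are cumulative. Item 4.2(g) deals with the condition and 4.3 with the drugs, and excluding uncontrolled hypertension does not declare everyone else eligible. Only the unclear breadth of the cardiovascular term remains.

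**Conclusion.** The plan contradicts itself on one safety exclusion. Sections 1.3.3.1.d and 4.2(a) give different answers for a past psychotic disorder outside the five named diagnoses, for such a disorder in an immediate relative, and for an affected relative outside the immediate family. The mismatch can operate twice, at first screening and at re-screening before open-label dosing.

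This rests on reading psychotic disorder in 1.3.3.1.d as a general category and family there as unrestricted, which is the ordinary sense of the words. It also assumes that 4.2 is the list the investigator would be expected to check. That is inferred from its heading and from the eligibility review, not from any clause giving it precedence.

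The size cannot be given. The documents say nothing about how common such histories are among candidates, and one participant's share of the sample would estimate nothing. A reader might also infer that the protocol calls these people unsafe to dose, or that such people will in fact be dosed. It says neither: it calls for their exclusion while rating the risk as very low, and other steps could still stop them. What is shown is a fault in the written rules that should be corrected. The cardiovascular wording is a lesser ambiguity.

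**What to change.** Reconcile 1.3.3.1.d and 4.2(a) so that a single wording of the psychosis exclusion and a single definition of family history appear in both and on the eligibility checklist, including the one used before open-label dosing. Which wording and which family scope are right is for the sponsor to settle.

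Second, state in 3.1.4 and 4.3 how the general cardiovascular term relates to the two named antihypertensives.

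The laboratory and breast-feeding exclusions and the age range could be copied into section 4 at the same time, as editorial consolidation only.

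The cost is protocol amendment wording and a revised checklist. No new assessment or procedure is needed. Any effect on recruitment depends on the wording chosen and cannot be estimated from the documents.
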